12.6. Subject Characteristics

12.6.1. Demographics

All dosed subjects enrolled in the study will be included in a listing of subject demographic characteristics. Summary statistics tables will present the data for all dosed subjects combined as well as for completers only.

12.6.2. Medical and Surgical History

The medical and surgical history data will not be summarized but will be presented in a data listing.

12.6.3. Concomitant Medications

Concomitant medications will not be summarized but will be presented in a data listing.

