4. OBJECTIVES

4.1. Primary Objective

Primary Objective	Primary Endpoints
To confirm the safety and tolerability of Acthar in the induction of remission of proteinuria in subjects with primary FSGS who are resistant to, or intolerant of, at least 1 prior immunosuppressive therapy	
 ● Severity and frequency of adverse events (AEs) ● Changes in physical findings ● Changes in clinical laboratory findings ● Changes in vital signs

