7.2. Permitted During Study

If any medication is taken during the study, all pertinent information will be recorded in source documents and the eCRF.

Subjects should remain on stable doses of ACEi and/or ARB during the study. An adjustment in the dose of these medications would represent a protocol deviation, but would not necessarily mandate study termination. Adjustments in dose of a concomitant medication should be documented in the subject's source documents and eCRF.

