9.3.1. Dose Reduction

The dosing of Acthar should be tapered from 3x/week to 2x/week for safety reasons if a subject meets any of the following criteria:

- Development of accelerated hypertension (defined as systolic blood pressure \geq 180 *and* diastolic blood pressure \geq 100 mm Hg) that cannot be managed with adjustment of concomitant medications such as antihypertensive medications.
- Development of an edema score of 4 at any visit that cannot be managed with adjustment of concomitant medications such as diuretics (see [Section 24.2](#)).
- Development of congestive heart failure that cannot be managed with adjustment of concomitant medications such as diuretics and antihypertensive medications.
- Development of diabetic signs/symptoms (ie, HbA1c > 8%, or fasting plasma glucose > 126 mg/dL, or classic symptoms of hyperglycemia with random plasma glucose > 200 mg/dL).
- Development of any other AE of at least moderate intensity that cannot be managed with adjustment of concomitant medications.

Any subject whose dose is tapered for any of the reasons described above will have a Taper Safety Visit scheduled 2 weeks after the start of the taper.

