9.3.2. Treatment Discontinuation

Treatment with Acthar should be discontinued for safety purposes if the reduction in dosing to 2x/week **and** adjustment of concomitant medications does not manage the following:

- Persistent accelerated hypertension (defined as systolic blood pressure ≥ 180 *and* diastolic blood pressure ≥ 100 mm Hg).
- Persistent edema score of 4 (see [Section 24.2](#)).
- Persistent congestive heart failure.
- Persistent diabetic signs/symptoms (ie, HbA1c $> 8\%$, or fasting plasma glucose > 126 mg/dL, or classic symptoms of hyperglycemia with random plasma glucose > 200 mg/dL).
- Any other AE of at least moderate intensity that cannot be managed with adjustment of concomitant medications.

The investigator should discontinue subjects for safety purposes any time during the study if the subject meets any of the following criteria:

- Development of unexplained and sustained (2 consecutive visits) worsening of disease defined as unresolved progression or 30% decline in eGFR from baseline, or if the subjects remains at significant risk of sequelae of nephrotic syndrome (such as serum albumin < 2.8 mg/dL) and sustained worsening of uPCR (increase $> 50\%$ from baseline).
- Development of ESRD and requirement for chronic renal replacement therapy.
- Administration of live or live-attenuated vaccines after Screening Visit/Visit 1.
- Diagnosis of a malignancy or lymphoproliferative disorder.
- Pregnancy during the course of the study.
- Development of an independent disease that requires treatment with immunosuppressive therapy or plasma exchange therapy.
- Development of a contraindication to IMP use.
- Use of any investigational drug, device, or procedure as part of a research study.

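### Section 12.6.3 rules out any summary of concomitant medications, although drug adjustment comes before most safety-related dose reductions and discontinuations and may attenuate the primary safety findings

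*Combined protocol and SAP*

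**What the plan says.** Section 12.6.3 is explicit: "Concomitant medications will not be summarized but will be presented in a data listing". This is a stated exclusion, not silence.

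Section 4.1 sets an objective of safety and tolerability. Its primary endpoints include "Changes in physical findings" and "Changes in vital signs", alongside adverse events and laboratory changes.

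Section 9.3.1 makes the safety taper from three to two injections a week conditional. Accelerated hypertension counts if it is one "that cannot be managed with adjustment of concomitant medications such as antihypertensive medications". The edema criterion reads "Development of an edema score of 4 at any visit that cannot be managed with adjustment of concomitant medications such as diuretics", and the heart-failure criterion "Development of congestive heart failure that cannot be managed with adjustment of concomitant medications such as diuretics and antihypertensive medications". A similar clause covers any other adverse event of at least moderate intensity. The diabetes criterion in 9.3.1 has no such clause.

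Section 9.3.2 applies its first list of discontinuation reasons, which includes persistent diabetic signs, if dose reduction together with "adjustment of concomitant medications does not manage the following".

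On-study stability is asked of ACE inhibitors and ARBs only. For those, Section 7.2 says "An adjustment in the dose of these medications would represent a protocol deviation".

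**The concern.** Section 3.5 names hypertension, hyperglycemia and worsening peripheral edema among the known risks of the product. For pressure and fluid effects, the taper criteria come into play only after drug adjustment has failed. Blood pressure, weight and edema may therefore be read after the subject's other drugs have changed.

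Two results become hard to interpret. Little change in blood pressure or edema could mean little product effect, or an effect offset by more antihypertensive or diuretic. Few tapers or discontinuations could mean good tolerability, or successful drug adjustment. With one open-label arm of about 60 subjects there is no control group to separate these. The number of subjects who needed more medication is the most direct evidence, and it is the item that 12.6.3 says will not be tabulated.

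**Working it through.** The documents give no sample-size, power or event-rate figure for this point (Section 12.9 says no formal calculation was done), so there is no plan figure to reproduce. The check is a side-by-side reading, followed by an illustration on assumed inputs.

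**Reading the sections together**

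1. Is the adjustment recorded? Yes. Section 7 collects start and stop dates, dose, frequency and indication. Section 7.2 requires dose adjustments to be entered in the source documents and the eCRF.
2. Is it reported? By listing only (12.6.3).
3. Are its consequences counted? Section 12.6.4 summarises discontinuations by reason. It specifies no table of tapers and no count of the drug adjustments that came first.
4. Does another table show it? Under Section 10.5, an out-of-range vital sign becomes an adverse event if the investigator finds it clinically significant or if it requires a change in management. Section 10.4 does the same for clinically significant examination changes. Section 12.7.1 tabulates treatment-emergent events by system organ class, preferred term and severity. That captures part of the effect but gives no count of subjects who needed more drug. Section 6.1 admits subjects with a mean pressure up to 150/90 mm Hg who already take other antihypertensives, so raising an existing drug need not produce a new event.
5. How are the affected endpoints reported? Sections 12.7.3 and 12.7.4 plan listings for examinations and for vital signs and weight. Section 12.4 speaks of a summary of the safety profile. No mean change is specified.

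**Illustration (all inputs assumed except n)**

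Let q be the share of subjects given a new or increased antihypertensive, and d the mean fall in systolic pressure this produces. If a mean change were reported, its attenuation would be q × d:

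| q | d = 5 | d = 10 | d = 15 | d = 20 mm Hg |
|---|---|---|---|---|
| 10% | 0.5 | 1.0 | 1.5 | 2.0 |
| 20% | 1.0 | 2.0 | 3.0 | 4.0 |
| 30% | 1.5 | 3.0 | 4.5 | 6.0 |
| 50% | 2.5 | 5.0 | 7.5 | 10.0 |

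For comparison, the 95% half-width of a mean change is 1.96 × SD / √n. With n = 60 (Section 5.4):

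- SD 10: 1.96 × 10 / 7.746 = 2.53 mm Hg
- SD 15: 3.80 mm Hg
- SD 20: 5.06 mm Hg

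The attenuation can therefore be smaller or larger than sampling error.

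**Precision of the proposed count (Wilson 95% interval, n = 60)**

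For 12 of 60, p = 0.20 and z² = 3.84. The denominator is 1 + 3.84/60 = 1.064. The centre is (0.20 + 3.84/120)/1.064 = 0.218. The half-width is 1.96 × √(0.16/60 + 3.84/14,400)/1.064 = 0.100. The interval is 11.8% to 31.8%. Likewise, 6 of 60 gives 4.7% to 20.1%, and 18 of 60 gives 19.9% to 42.5%. That is precise enough to be useful descriptively.

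**The case against.** The strongest reply has four parts.

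- **Many treated rises should already be tabulated.** Starting or raising a drug for an out-of-range pressure is a change in management, so Section 10.5 makes it an adverse event, and adverse events are the first-listed primary endpoint. This stands in part. The route depends on an out-of-range value and on investigator judgement, and its tables do not give the number of subjects who needed more medication.
- **No mean change is specified, so none can be distorted.** Vital signs and examinations are themselves only listed. This stands, and listing-only output for primary endpoints is a more basic gap. It does not remove the present point: if the summary mentioned in 12.4 is produced, it needs the medication context, and discontinuation counts are affected either way.
- **The treatment is reported, in a listing.** True, but a subject-level listing across up to 50 weeks of visits does not give a reader the count.
- **Sections 9.3.1 and 9.3.2 do not order anyone to add drugs.** A reader might infer that investigators must first treat these effects with added drugs. The text does not say so. It sets a condition on dose reduction and discontinuation, speaks of adjustment, and for blood pressure and edema concerns defined severe states (systolic at least 180 and diastolic at least 100 mm Hg; edema score 4). ACE-inhibitor and ARB doses are meant to stay fixed.

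**Conclusion.** The point holds as a reporting gap that should be closed. Drug adjustment comes before most safety tapers and before the first group of discontinuation reasons. It may attenuate observed blood pressure, weight and edema changes and lower taper and discontinuation counts, and the plan expressly declines to tabulate it.

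A reader might go further and infer that the primary vital-sign and physical-finding changes will be masked. The documents do not support that. Medication data are collected and listed, many treated rises will enter the adverse-event tables, and neither the frequency of adjustment nor its effect is given. The range of 0.5 to 10 mm Hg rests wholly on assumed values (10% to 50% treated, 5 to 20 mm Hg effect) and shows only that material attenuation is possible. The case is strongest for antihypertensives and diuretics. For glucose-lowering drugs it rests on 9.3.2, because the diabetes criterion in 9.3.1 carries no drug-adjustment clause. No view is taken on the clinical rules themselves.

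**What to change.** Amend Section 12.6.3 as follows.

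- Keep the listing.
- Add one descriptive table of the number and percentage of dosed subjects who start or increase an antihypertensive, diuretic or glucose-lowering drug after the first dose. Show it by class and by visit interval, with a 95% confidence interval for the overall percentage.
- In any summary or listing of vital signs, weight and edema under 12.4, 12.7.3 and 12.7.4, flag values obtained after such a change.

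Do not add a table of blood pressure, weight or glucose change split by whether medication changed. Subjects receive more drug because the measurement rose, so the split conditions on a consequence of the outcome. Neither group would recover the untreated change, and a group could be small (12 subjects if 20% of 60 are treated). Lipid-lowering drugs are left out because neither 9.3.1 nor 9.3.2 mentions lipids.

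The cost is medication coding and modest programming. Sections 7 and 7.2 already collect the data, and no clinical rule changes.

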12.6.4. Subject Disposition and Exposure to IMP

The number of subjects who complete the study and who do not complete the study, both overall and according to reasons for discontinuation from the study, will be summarized for all dosed subjects. Subject disposition will be presented in a data listing.

12.7. Safety Analysis

All subjects who receive at least 1 dose of IMP will be included in the safety analyses.

12.7.1. Adverse Events

AEs will be coded using MedDRA. All AEs will be presented in a data listing. Only treatment-emergent adverse events (TEAEs) will be included in all summaries.

TEAEs, treatment related TEAEs, severity of TEAEs, and TEAEs leading to early discontinuation will be summarized by system organ class and preferred term for all dosed subjects at the treatment level and overall. All TEAEs leading to early discontinuation will be presented in data listings.

12.7.2. Clinical Laboratory Tests

Clinical laboratory testing will be presented in data listings.

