12.4. Primary Safety Endpoints

The primary safety endpoints to be evaluated include a summary of the general safety profile including AEs (serious and non-serious), physical examinations, clinical laboratory tests, vital signs, medical and surgical history, height and weight.

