12.7.3. Physical Examination Findings

All physical examination results will be presented in a data listing.

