12.7.4. Vital Signs/Height and Weight

Vital sign measurements (diastolic blood pressure, systolic blood pressure, respiratory rate, pulse rate, body temperature, weight and height) will be presented in a data listing.

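### Three of the four primary safety endpoints are changes in findings, but their own analysis sections state only data listings, and the section headed for exposure contains no exposure or dose-reduction summary

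*Combined protocol and SAP*

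**What the plan says.** Section 4.1 and the Synopsis list four primary endpoints: severity and frequency of adverse events (AEs), and changes in physical findings, in laboratory findings and in vital signs. The laboratory item reads "Changes in clinical laboratory findings".

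The planned outputs are in 12.7. Section 12.7.1 gives AEs a listing and also summaries of treatment-emergent AEs (TEAEs) by system organ class and preferred term. The other three domains get one sentence each:

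- Laboratory (12.7.2): "Clinical laboratory testing will be presented in data listings".
- Physical examination (12.7.3): "All physical examination results will be presented in a data listing".
- Vital signs (12.7.4), at the end of a list of measurements: "weight and height) will be presented in a data listing".

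Two general provisions bear on this. Section 12.1 sets default statistics for continuous variables (n, mean, SD, median, minimum, maximum) and counts with percentages for categorical ones, and says that analysis will follow the SAP. Section 12.4 describes the primary safety endpoints as a summary of the safety profile that includes AEs and "physical examinations, clinical laboratory tests, vital signs, medical and surgical history, height and weight".

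Section 12.6.2 says of one item in that list: "The medical and surgical history data will not be summarized but will be presented in a data listing". Section 12.6.3 is equally explicit: "Concomitant medications will not be summarized but will be presented in a data listing".

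Section 12.6.4 is headed for disposition and exposure. Its text summarises "The number of subjects who complete the study and who do not complete the study, both overall and according to reasons for discontinuation" and adds a disposition listing. It does not mention duration of exposure, doses taken or dose reductions.

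**The concern.** A listing shows each subject's values. It does not report a change, and change is what three primary endpoints are defined to be. Demographics (12.6.1), disposition (12.6.4) and AEs (12.7.1) each have an explicit summary, so the analysis sections commit to less for these three endpoints than for baseline characteristics.

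Section 3.5 names hypertension, hyperglycemia and worsening peripheral edema as known risks. These are measured repeatedly, and a gradual shift across the group shows in by-visit change or shift tables. It may never appear as a reported event. Sections 10.4, 10.5 and 10.7 route clinically significant changes into AE reporting, but the investigator judges significance, and the study is unblinded (9.2).

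On exposure, tolerability is part of the primary objective. Reduction from three to two injections a week is allowed for safety or tolerability and is then permanent (3.3, 5.1). The number reduced, and when, is a direct tolerability result, and the visible Section 12 does not ask for it. Section 12.7.1 also summarises TEAEs by a treatment level that it does not define in a single-treatment study. If dosing frequency is meant, exposure by frequency is the missing denominator.

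**Working it through.** There is no stated power or precision figure to reproduce; 12.9 says no formal sample size calculation was done.

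**1. Endpoint against planned output.**

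| Primary endpoint (4.1) | Own analysis section | Output stated there |
|---|---|---|
| AE severity and frequency | 12.7.1 | Listing and summaries |
| Changes in laboratory findings | 12.7.2 | Listing |
| Changes in physical findings | 12.7.3 | Listing |
| Changes in vital signs | 12.7.4 | Listing |

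Three of four have only a listing in their own section. No visible text in Section 12 defines a baseline, a change score, a visit summary, a shift table or an abnormality threshold for them. Section 12.5 is redacted and cannot be checked.

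**2. Are the data collected?** Table 1, treatment visits after the first dose:

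- Vital signs and limited examination: Visits 3 to 15 = 13. The limited examination includes edema (10.4), scored 0 to 4 (Attachment 2).
- Chemistry and hematology: Visits 3 to 8 (6) + Visits 10 to 15 (6) = 12.
- HbA1c by its own row: Weeks 12, 24, 38 and 50 = 4, with Screening the only pre-dose draw. Attachment 1, however, lists HbA1c under Serum Chemistry, which Table 1 schedules at Visit 2 and at those 12 later visits. The two do not agree.

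**3. How far can exposure differ among completers?** Inputs: 3 doses a week, or 2 after reduction, over 50 weeks (5.1, Table 5). The reduction week w is assumed. Scheduled doses = 3w + 2(50 − w).

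| Case | Doses in 50 weeks | Shortfall |
|---|---|---|
| Never reduced | 3 × 50 = 150 | – |
| Reduced at Week 4 | 12 + 92 = 104 | 46/150 = 30.7% |
| Reduced at Week 24 | 72 + 52 = 124 | 26/150 = 17.3% |

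The end-of-treatment taper (2 × 2 = 4 doses) is left out because it applies only to subjects still on three doses a week. A disposition table counts all three subjects as completers.

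**4. Would the tables be informative at this size?** This concerns the value of the fix, not the size of the defect, and the inputs are assumptions. For mean blood pressure change, the 95% half-width is t(0.975, n − 1) × SD/√n. With an SD of change of 10 to 20 mm Hg it is 2.6 to 5.2 mm Hg at n = 60 and 3.7 to 7.5 at n = 30. If 12 of 60 subjects were reduced (20%), the exact 95% interval is 10.8% to 32.3%.

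**The case against.** A reader might infer that the protocol plans no summary of these endpoints, or rules one out. The documents do not support that. The defaults in 12.1 apply unless otherwise noted, and laboratory values and vital signs are continuous. Section 12.4 speaks of a summary covering these domains. Sections 12.7.2 to 12.7.4 lack the explicit exclusion found in 12.6.2 and 12.6.3. The SAP to which 12.1 defers may contain every table asked for here.

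All of that stands, and it limits the point. It does not remove it. The 12.1 defaults are tied to no endpoint, visit or baseline, and a section that names only a listing can be read as the exception. Section 12.4 names domains and not an analysis. It also includes medical history, which 12.6.2 says will not be summarized, so it cannot settle how the other sections should be read.

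The AE route is also firmer than simple investigator choice. Clinically significant examination changes must be recorded as AEs, a vital-sign change that requires altered management also counts, and the significance of each laboratory abnormality must be documented. For most examination findings, TEAE tables are a reasonable summary. The route still omits changes below those thresholds.

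Counting the four taper doses for the never-reduced subject would raise the shortfalls to 50/154 = 32.5% and 30/154 = 19.5%. That compares unequal periods; the 50-week figures are the fair ones.

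**Conclusion.** The point holds as a mismatch within the protocol. Three of four primary endpoints are defined as changes, and their own sections state only listings. The general text in 12.1 and 12.4 points towards a summary without specifying change from baseline, visits or shifts. It does not follow that a summary is absent from the whole plan or prohibited.

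The exposure gap is plainer: 12.6.4 does not deliver what its heading names, and no other visible part of Section 12 does. The 30.7% and 17.3% shortfalls rest on assumed reduction times and on scheduled doses, not doses taken. They show how different two completers can be, not how often that happens.

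What cannot be known from the supplied document is whether the SAP closes either gap. This is a cheap improvement.

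**What to change.** - **12.7.2 and 12.7.4:** alongside the listings, add observed value and change from the last pre-dose value, by visit, using the 12.1 statistics. For laboratory tests add low/normal/high shift tables.
- **12.7.3:** add a shift table of edema score from the last pre-dose assessment, and state that other clinically significant examination changes are summarised through TEAEs.
- **12.6.4:** add duration of exposure by dosing frequency, and n (%) with a safety or tolerability dose reduction, counted separately from the end-of-treatment and early-termination tapers.
- **12.7.1:** define the treatment level used in the TEAE summaries.
- **12.4:** reconcile with 12.6.2 on medical history and with 12.7.2 to 12.7.4 on what is summarised.
- **HbA1c:** use the last pre-dose value, and reconcile Table 1 (separate row, not at Visit 2) with Attachment 1 (under Serum Chemistry, drawn at Visit 2).

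If the SAP already specifies these tables, a citation to it in 12.6.4 and 12.7 is enough for them; the inconsistencies within the protocol still need correcting.

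The cost is wording and a few standard safety tables. Laboratory, vital-sign and edema data are already scheduled, and the diary records all dosing (9.7), so no new subjects, visits or procedures are needed.
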